14.3 Additional Descriptive Analysis on IAQ Parameters

During the review and finalization of results from the analysis of the IAQ parameters, it was identified that pre-event data was available but not analyzed. For each of the IAQ parameters that were collected in the study, we will calculate descriptive statistics for the parameters to obtain information about background levels of the various analytes.

14.4 Additional Secondary Analysis on IAQ Parameters Performed by CRO

During the review and finalization of the results from the secondary analysis of the IAQ parameters it was identified that there was a discrepancy between the SAP specified model and the results provided by the CRO [REDACTED]. The planned model, uses observations collected at each timepoint for each events in the model however [REDACTED] used a model with endpoints averaging observations from each event.

This was due to an incorrect model specification in section 11.6.2.1.1. which did not allow the specified model to converge. Results from this additional analysis will be kept and presented in the Appendix of the study report.

14.5 Additional Analysis to Explore Effect of Heatstick Consumption on Urinary BoExp

14.5.1 Effect of HeatStick Consumptions on Urinary BoExp in Compliant Exposure Set

During the review of the Clinical Study Report questions were raised about the relationship between HeatStick consumption and the levels of BoExp in the Compliant Exposure Set. A prior post-hoc analysis (14.2) investigated the effect of HeatSticks consumption and other covariates such as food consumption and consumption of alcoholic beverages on carbonyls in air. To corroborate the results from that analysis and impact of HeatSticks on the urinary BoExp, we will use the models developed for the BoExp (12.6.1.1, 12.6.2.2) and include a covariate for total HeatSticks consumption used during an Event. As with the existing models for the BoExp, the estimates for each product use group will be exponentiated and reported as geometric means and the ratio of geometric lsmeans between Exposure and Non-Exposure Events will be calculated and reported together with its 95% confidence intervals.

A sample of the code is presented below,

```
Proc mixed data=_data_ method=reml;
Class event_type sex product_use;
Model endpoint = baseline sex event_type product_use event_type*product_use
duration cumulative_heatsticks product_use*cumulative_heatsticks<IAQ covariates>
/ ddfm=kr;
estimate 'Cigarette Smoker Exposure event' intercept 1 baseline xx sex .5 .5
product_use 1 0 0 event_type 1 event_type*product_use 1 0 0 0 0 0 duration xx
cumulative_heatsticks xx IAQ1 xx ... IAQn xx / alpha=0.05 cl;
estimate 'Cigarette Smoker Non-Exposure event' intercept 1 baseline yy sex .5 .5
product_use 1 0 0 event_type 0 event_type*product_use 0 0 0 1 0 0 duration yy
cumulative_heatsticks 0 IAQ1 yy ... IAQn yy / alpha=0.05 cl;
estimate 'Cigarette Smoker Exposure vs Non-Exposure event' intercept 0 baseline
xx-yy sex 0 0 product_use 0 0 0 event_type 0 event_type*product_use 1 0 0 -1 0 0
duration xx-yy cumulative_heatsticks xx IAQ1 xx-yy ... IAQn xx-yy / alpha=0.05 cl;
Run;
```

We define xx as the average values of a covariate for a participant belonging to the product use group of interest during an Exposure Event and yy as the corresponding average during a Non-Exposure Event. If the model fails to converge, then the individual exposure to HeatSticks based on the duration a participant was in the Exposure Event will be calculated and this will be used in place of an overall cumulative exposure to HeatSticks during the entire Exposure Event. The value of xx in this case would be the average of all the individual exposures to HeatSticks for each participant.

This analysis will be repeated for all endpoints listed in Table 8.

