12.6 Planned Statistical Analyses

12.6.1 Primary Analysis

12.6.1.1 Statistical Analysis of Primary Endpoints

For each urinary BoExp in the primary analysis NEQ, Total NNAL, Total NNN, the change between pre-event and end of study levels adjusted for creatinine will be modeled using a linear model in the Compliant Exposure Set.

The SAS procedure PROC MIXED will be used with the restricted maximum likelihood method for estimation of the parameters. The mixed model will have the change from baseline as dependent variable and the following covariates will be included in the model: Baseline, Sex, Event Type (Exposure or Non-Exposure), Duration of Exposure, Product Use Status, Product Use Status by Event Type interaction for all BoExp. In addition, an air quality covariate related to each BoExp is included in the model depending on the endpoint and is described in Appendix 15.2. This table also specifies the various IAQ covariates that are assessed using a step-wise regression approach for each BoExp. The algorithm is described below,

1. Fit a full model with all covariates

2. Drop one IAQ covariate and re-fit the model.
3. Perform a likelihood ratio test and drop the IAQ covariate with the largest p-value for the likelihood ratio statistic if it is more than 0.05.
4. Repeat steps 2 and 3 until no more IAQ covariates can be dropped.
5. Refit the final model with the IAQ covariates remaining in the model and estimate exposures for each product use group.

Appropriate contrasts will be constructed to determine the effect of passive exposure to IQOS aerosol during the Exposure Event on the mean change in levels of urinary BoExp together with the 95% CIs for non-smokers during an Exposure Event. Other contrasts can be constructed to determine the change in urinary BoExp for participants with other smoking status (Cigarette Smoker and IQOS Passive Users) after passive exposure to IQOS usage.

An example of SAS code for the final model is provided below,

```
Proc mixed data=_data_ method=reml;
Class event_type sex product_use;
Model endpoint = baseline sex event_type product_use event_type*product_use
duration <IAQ covariates> / ddfm=kr;
estimate 'Cigarette Smoker' intercept 1 baseline xx sex .5 .5 product_use 1 0 0
event type 1 event_type*product_use 1 0 0 0 0 duration xx IAQ1 xx ... IAQn xx /
alpha=0.05 cl;
Run;
```

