**Table 8. Covariates for Analysis of Urinary BoExp**

Endpoint	Included Covariates ¹	Included Air Quality Covariates ¹	Evaluated Air Quality Covariates
S-PMA	Baseline, Sex, Event Type, Duration of Exposure, Product Use Status, Product Use Status by Event Type	NNK	Formaldehyde, Acetaldehyde, Acrolein, Crotonaldehyde, 3-ethenylpyridine, PM2.5, and PM10
HEMA	Baseline, Sex, Event Type, Duration of Exposure, Product Use Status, Product Use Status by Event Type	NNK	Formaldehyde, Acetaldehyde, Acrolein, Crotonaldehyde, 3-ethenylpyridine, PM2.5, and PM10

1 These covariates will be included in the statistical models for their respective urinary BoExp

2 The covariates pertaining to air quality will be assessed as described in Section 12.6.1.1

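### SAP 14.5.1 was added to relate HeatStick consumption to bystanders' urinary biomarkers, but the outputs it names carry no HeatStick dose information and the HeatStick slope is not listed for reporting.

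*SAP*

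**What the plan says.** SAP 14.5.1 explains that during review of the study report "questions were raised about the relationship between HeatStick consumption and the levels of BoExp in the Compliant Exposure Set", and that the added analysis should corroborate the post-hoc air analysis in 14.2. The method is stated as follows: "we will use the models developed for the BoExp (12.6.1.1, 12.6.2.2) and include a covariate for total HeatSticks consumption used during an Event". The sample MODEL line contains "duration cumulative_heatsticks product_use*cumulative_heatsticks<IAQ covariates>", so HeatSticks, their interaction with product use and the air covariates stand together.

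The air covariates come from the parent model, where "an air quality covariate related to each BoExp is included in the model depending on the endpoint". The first footnote of Table 8 (SAP 15.2) makes this mandatory: "These covariates will be included in the statistical models for their respective urinary BoExp". The forced marker is air nicotine for NEQ, NNK for Total NNAL, S-PMA and HEMA, NNN for Total NNN, crotonaldehyde for HMPMA and acrolein for 3-HPMA. Other air markers enter and may be dropped by backward elimination.

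For output, 14.5.1 names exponentiated estimates per product-use group and says "the ratio of geometric lsmeans between Exposure and Non-Exposure Events will be calculated and reported together with its 95% confidence intervals". It names no slope, per-stick effect or interaction estimate. The sample code has no ESTIMATE line for one and does not request `solution`, although the code in 14.2 and 14.5.2 does.

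**The concern.** The analysis exists to say whether bystanders' biomarkers move with the amount of product used around them. A result that does not depend on the HeatStick term cannot say that. A reader of Table 15.2.2.7.5 could take its ratio for a HeatStick effect, or for an event effect adjusted for HeatSticks. It is neither. It is the event-type comparison of 14.1 over again.

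The coefficient that would answer the question has its own difficulty. The Compliant Exposure Set may use no product during an Event, so other people's HeatSticks reach their urine through room air. A model that holds an air marker fixed estimates only the part of the HeatStick effect that the marker does not explain.

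**Working it through.** The SAP gives no numerical result or precision target for this analysis, so there is no stated figure to reproduce.

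**1. What the named outputs depend on.** The model has a free parameter for each event-type by product-use cell and no random effects (SAP 10 removes the subject effect). Residuals therefore sum to zero in each cell, and the fitted value at a cell's covariate means equals that cell's mean response. Let ȳ be the cell mean on the log scale, s the proportion of one sex, γ the sex coefficient, E and N the event types and p the product-use group. The code sets sex at 0.5/0.5 for the means and at zero for the contrast, and sets baseline, duration, HeatSticks and air markers at group means. Then:

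- Exposure mean for group p = ȳ(E,p) − γ[s(E,p) − 0.5]
- log ratio for group p = ȳ(E,p) − ȳ(N,p) − γ[s(E,p) − s(N,p)]

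No HeatStick or air coefficient appears. Adding HeatSticks can change the 14.1 ratio only by altering γ. A further small shift arises if air values are averaged over events instead of participants.

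**2. Numerical check.** The values here are assumed, not taken from the documents: 169 participants per event type, 80 to 160 sticks per Exposure Event, total effect 0.30 log units per 100 sticks, residual SD 0.5, no sex term, 600 runs per setting. The expected contrast at a mean of 120 sticks is 0.30 × 1.20 = 0.36. The simulated contrast was 0.355 to 0.366 across settings. Within every run, the fit with HeatSticks plus the air marker and the fit with the air marker alone differed by 0.000.

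**3. What the unlisted slope would be.** Same simulation, four Exposure Events. Ranges are over air-marker noise of 0.1 and 0.3, on a scale where 100 sticks raise the marker by 1.

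| Share of effect through the marker | Slope, no air marker | Slope, marker forced | SE, no marker | SE, marker forced |
|---|---|---|---|---|
| 0% | 0.285–0.297 | 0.276–0.327 | 0.199–0.204 | 0.278–0.521 |
| 50% | 0.301–0.326 | 0.155 | 0.197–0.204 | 0.271–0.509 |
| 100% | 0.294–0.310 | 0.001–0.006 | 0.202–0.207 | 0.286–0.520 |

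With three Exposure Events the pattern is the same. The forced-marker slope is −0.024 to 0.008 under full mediation and 0.126 to 0.171 under half. Across all settings the SE rises 1.3-fold (0.271/0.204) to 2.8-fold (0.618/0.219).

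A second simulation added error in the air measurement, assuming full mediation, 20 people of one group per event, about 200 sticks per Exposure Event (SD 40) and 10% ventilation variation. The median slope without the marker was about 0.31. With the marker forced it was −0.01, 0.07, 0.16 and 0.26 at 0, 5, 10 and 20% measurement error.

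**4. How much information there is.** SAP 12.6.2.1.1 lists four Exposure and two Non-Exposure Events; Protocol Table 5 shows three and two. Because event type is in the model, the zero sticks at Non-Exposure Events do not inform the slope. Only differences among Exposure Events do. With six events, intercept, event type and HeatSticks leave 6 − 3 = 3 event-level degrees of freedom, and the forced marker leaves 2. With five events the figures are 2 and 1.

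At SE 0.20, an estimate of 0.30 has a 95% interval of 0.30 ± 1.96 × 0.20 = −0.09 to 0.69, or a ratio of 1.35 (0.91 to 2.00) per 100 sticks. With equal residual SD, group slopes are less precise: about 0.20/√0.50 = 0.28 for Non-Smokers and 0.20/√0.25 = 0.40 for each other group.

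These SEs ignore event-to-event variation. In the second layout, nominal 95% intervals from the fit without air markers or an event term covered the true slope 90–92% of the time at 10% ventilation variation and 71–72% at 30%.

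**5. Sample code.** The Non-Exposure line and the ratio line set the `event_type` coefficient to zero, and a design-matrix check shows neither is estimable as written. Step 1 assumes this is corrected and that the HeatStick interaction gets the group's own mean dose. The code is labelled a sample, so this is secondary.

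**The case against.** The strongest reply is that over-adjustment reaches no output the SAP names. The contrast adds the air-marker difference back, and step 1 shows that the ratio is unaffected. That stands. A reader might infer that forcing the air markers biases the reported ratio, or that the plan will yield a false finding that HeatSticks add nothing. The documents do not support either: the coefficient that could be pulled toward zero is one the SAP does not plan to show.

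A reader might also infer that every forced marker is a known product emission. Protocol 2.1.1 reports that, of 23 analytes, only nicotine and acetaldehyde, with glycerin, were detectable in air after IQOS use. Nicotine is forced for NEQ alone, and acetaldehyde is never forced. Abundance in the aerosol is one of four marker-selection criteria in Protocol 4.3, which does not show that each marker rises in room air. For S-PMA and HEMA, the forced NNK is not even the parent compound.

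The attenuation also depends on assumptions. The covariate is an area average starting an hour after the last entry, not a personal dose, and 20% measurement error left 0.26 of the 0.30.

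Further, the analysis is post hoc, the study tests no hypotheses (SAP 6.3.1), and the table shells are a separate document that might contain a slope. If the model fails to converge, 14.5.1 falls back on individual HeatStick exposure, which varies within events. These points limit the consequence. They do not supply the missing result: neither the fallback nor the title of Table 15.2.2.7.5 mentions a slope.

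**Conclusion.** The concern holds as a gap between the question and the named outputs. Followed exactly, 14.5.1 essentially repeats the 14.1 ratio and says nothing about HeatStick dose. This follows algebraically from the model, given corrected ESTIMATE lines and covariates at group means, and does not depend on simulated values.

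The air-marker adjustment matters only if the slope is printed. For NEQ it would pull the slope toward zero to the extent that the effect runs through air nicotine: from 0.30 to about 0.00 under full mediation, about 0.16 under half, and no distortion under none. Those sizes rest on assumed inputs. For the other endpoints the adjustment is a caution, not a documented effect. Any slope will be imprecise, because at most four Exposure Events inform it.

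**What to change.** In 14.5.1, fit the model without `<IAQ covariates>`, add a random event effect (or another event-level variance term), and report the HeatStick slope for each product-use group in Table 15.2.2.7.5, exponentiated per 100 sticks with its 95% CI. For example, use `event` in CLASS, `random event`, `solution`, and `estimate` lines of the form `cumulative_heatsticks 100 product_use*cumulative_heatsticks 100 0 0`. Report the slope from the fallback fit too, if that is used.

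State that only four Exposure Events inform the slope and that it is exploratory. If the air-adjusted fit is kept, show it separately, labelled as the HeatStick effect not explained by the measured air marker. Say that the Exposure/Non-Exposure ratio is not a HeatStick effect, and correct the non-estimable ESTIMATE lines.

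The cost is a few lines of SAP text and one extra fit per endpoint, with no new data. The downside is a wide interval, which reflects how little the events can tell.

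### SAP 14.5.1 fits a separate HeatStick slope for each product-use group, but its text and ESTIMATE lines do not match, so a group's own slope is never selected

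*SAP*

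**What the plan says.** SAP 14.5.1 was added after questions raised during review of the study report. It takes the existing biomarker models and proposes to "include a covariate for total HeatSticks consumption used during an Event". The text mentions no interaction. On output, it says that "the estimates for each product use group will be exponentiated and reported as geometric means", together with Exposure to Non-Exposure ratios and 95% confidence intervals.

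The sample code goes further than the text. The CLASS statement is "Class event_type sex product_use", so cumulative HeatSticks is continuous. The MODEL statement has both the main effect and an interaction: "duration cumulative_heatsticks product_use*cumulative_heatsticks<IAQ covariates>".

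The HeatStick parts of the three ESTIMATE lines, shown for Cigarette Smokers, are:

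- Exposure: "cumulative_heatsticks xx IAQ1 xx ... IAQn xx / alpha=0.05 cl"
- Non-Exposure: "cumulative_heatsticks 0 IAQ1 yy ... IAQn yy / alpha=0.05 cl"
- Exposure versus Non-Exposure: "duration xx-yy cumulative_heatsticks xx IAQ1 xx-yy ... IAQn xx-yy / alpha=0.05 cl"

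None of them names `product_use*cumulative_heatsticks`. The section defines xx as the covariate average in the product-use group of interest during an Exposure Event. It closes: "This analysis will be repeated for all endpoints listed in Table 8". Table 8 lists seven biomarkers, including the three co-primary ones.

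**The concern.** Text, MODEL and ESTIMATE describe different analyses. The text and the ESTIMATE lines fit a common slope. The MODEL statement has group-specific slopes. If the MODEL statement is what was meant, an estimate for a named group at xx sticks has to use that group's slope, and the printed lines do not ask for it.

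At stake is the Non-Smoker row, the group that the study is mainly about. Under one reading the row cannot be estimated. Under the other it would be labelled Non-Smoker but would carry the slopes of Cigarette Smokers and IQOS Passive Users, and nothing in the output need show this.

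**Working it through.** The plan gives no figure to reproduce. The check has two parts: which linear functions the printed lines define, and how large the effect could be.

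**1. Estimability.** A participant in group g who attends an event with h sticks contributes h to the `cumulative_heatsticks` column and h to the group-g column of the interaction. In every row of the design matrix, the three interaction entries therefore add up to the main-effect entry. Any estimable function must keep that equality.

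| Line | HeatStick coefficient | Interaction at zero | Equal spread (xx/3 each) | Own position (xx 0 0) |
|---|---|---|---|---|
| Exposure | xx | sum 0, not xx: non-estimable | sum xx: estimable, mean slope | sum xx: estimable, own slope |
| Comparison, `event_type` repaired | xx | non-estimable | estimable, mean slope | estimable, own slope |
| Non-Exposure, `event_type` repaired | 0 | estimable | same | same |

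A numerical check gave the same pattern. It used 338 participants (169 per event type, groups 25/25/50%), four Exposure and two Non-Exposure Events, and one IAQ covariate. The design matrix had 21 columns and rank 13.

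**2. The separate `event_type` fault.** The `event_type` coefficients must add up to the intercept coefficient and agree with those of `event_type*product_use`. The Non-Exposure line has intercept 1 but `event_type 0`. The comparison line has `event_type 0` against interaction coefficients 1 0 0 -1 0 0. Both are non-estimable as printed, whatever is done about HeatSticks. They need `event_type 0 1` and `event_type 1 -1`. The Exposure line does not have this fault.

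**3. Illustrative size for Non-Smokers under equal spread.**

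Inputs from the documents:
- 169 passively exposed participants, split 50/25/25% (SAP Table 1). This gives n = 84.5 Non-Smokers and 42.25 in each other group.
- Four Exposure Events (SAP 12.6.2.1.1).
- Three product-use groups (SAP 12.6.1.2).

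Assumed inputs: residual SD 0.5 log units, four equally spaced event totals with mean 200, and no adjustment for the other covariates.

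Because HeatSticks are 0 at every Non-Exposure Event and `event_type*product_use` is in the model, each slope is identified only by differences among the Exposure Events. With V the variance of the event totals:

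- Own slope: the estimate is the group mean at its own xx. SE = 0.5/√84.5 = 0.054.
- Mean slope: the estimate is that group mean plus xx × (mean slope − own slope). The extra variance is (xx²/V) × [(4/9)(0.25/84.5) + 2 × (1/9)(0.25/42.25)] = (xx²/V) × 0.00263.

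Totals 150 to 250: V = (2 × 50² + 2 × 16.67²)/4 = 1389. The extra SD is 200/37.27 × 0.0513 = 0.275. SE = √(0.275² + 0.054²) = 0.28. With no effect at all, the 95% sampling range of the geometric estimate is exp(±1.96 × 0.28), about 0.58 to 1.7.

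Totals 180 to 220: √V = 14.91. The extra SD is 200/14.91 × 0.0513 = 0.688, so SE = 0.69.

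**4. Bias.** Bias = xx × (mean slope − own slope), which is zero when slopes are equal. If only Non-Smokers have a slope, of 0.001 per stick, then at 200 sticks the bias is 200 × (0.001/3 − 0.001) = −0.133 log units. Since exp(−0.133) = 0.875, the estimate is 12.5% too low.

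**The case against.** The strongest reply is that this is sample code. It uses placeholders and shortened coefficient lists, and the executed program may differ. That stands: the documents cannot show what was run. But the code is the only place where the interaction is specified, and the text disagrees with it. SAP 14.4 also records that an incorrect model specification in the SAP led to a different model being run for the air-quality data.

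Second, the error may lie in MODEL. The text and all three ESTIMATE lines agree with a common slope. If that was intended, the HeatStick term on the Exposure line is right as printed. This also stands, and it is why the point is an inconsistency to reconcile, not a proven error in one statement.

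A reader might infer more than the documents support:

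- *That reported estimates certainly use the average slope.* This depends on how the software fills omitted coefficients, which neither document states. With zero fill, no number is produced.
- *That the estimates are biased.* With equal slopes the bias is zero and only precision suffers. The planned 95% confidence intervals would show that loss.
- *That the figures above describe this trial.* Neither document gives a HeatStick total or a residual SD. If the model fails to converge, SAP 14.5.1 switches to HeatStick exposure calculated per individual, which the illustration does not cover.
- *That the primary analysis is affected.* The model in SAP 12.6.1.1 has no HeatStick term.

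**Conclusion.** The inconsistency holds. With the interaction in MODEL, the Exposure line is either non-estimable or built on the unweighted mean of three slopes. The comparison line follows once `event_type` is repaired. The Non-Exposure line is unaffected by this omission.

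Under the stated assumptions the loss of precision is about fivefold (0.28/0.054 = 5.2) and grows as the event totals become more alike. Bias needs slopes that differ between groups. The consequence is confined to a supportive post-hoc result, tabulated separately as Post-Hoc3 in SAP 15.4. It should still be corrected, because the analysis covers all seven biomarkers and the correction is cheap.

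**What to change.** Make text, MODEL and ESTIMATE agree, by one of two routes:

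1. Common slope, as the text says: delete `product_use*cumulative_heatsticks` from MODEL.
2. Group-specific slopes: keep the interaction, state it in the text, and add `product_use*cumulative_heatsticks` with xx in the group's own position on the Exposure and comparison lines (xx 0 0 for Cigarette Smokers, the matching position for each other group).

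Under either route, also set `event_type` to 0 1 on the Non-Exposure line and 1 -1 on the comparison line. Adding the HeatStick coefficient alone leaves the comparison line non-estimable.

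The cost is a few code edits, one sentence of text and a rerun for seven endpoints. No new data are needed.

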8.2.1 Primary and Secondary Analysis of Urinary Biomarkers of Exposure

- Carbonyls: Acetaldehyde, Acrolein, Crotonaldehyde and Formaldehyde
 - At each event there are 3 machines where each collects 1 sample at 1 hour intervals over a 3 hour period.
 - All readings will be averaged over the 3 hour interval of an event and taken as one observation for all participants of the particular event.
- ISO measurement standards for ETS: 3-Ethenylpyridine (3-EP)
 - At each event there are 3 machines where each collects 2 samples at 3 hour intervals.
 - All readings from the 3 machines will be averaged and taken as one observation for all participants of the particular event.
- Real-time measurements of PM2.5 and PM10 suspended particles in air.
 - At each event there are 2 dedicated sensors measuring suspended particulate matter with a 1 minute interval monitoring.
 - For passively exposed participants we define the start time of exposure as the time of entry to the event room and end time of exposure as the time of collection of last urine sample. The exposure duration is defined as the start to end time of exposure for a participant. For each type of particulate matter (PM2.5 and PM10), the reading associated with a particular participant will be the average of all the readings from the 2 sensors depending on the participant's exposure duration.
 - For actively exposed participants we define the start time of exposure as the start time of first IQOS use and end time of exposure as the time of collection of last urine sample. The exposure duration is defined as the start to end time of exposure for a participant. For each type of particulate matter (PM2.5 and PM10), the reading associated with a particular participant will be the average of all the readings from the 2 sensors depending on the participant's exposure duration.

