10 CHANGES FROM THE PROTOCOL SPECIFIED STATISTICAL ANALYSES

For the primary and secondary analysis, the random subject effect is removed as there are no repeated measures.

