12.6.2.1.1 Carbonyls

During each Exposure and Non-Exposure Event, there are 3 sampling cases that collects air for the assessment of carbonyls at 1 hour intervals. Each sampling case was placed at the same location during an Event.

The SAS procedure PROC MIXED will be used with the restricted maximum likelihood method for estimation of the parameters. The mixed model will have the carbonyl reading as dependent variable and the following covariates will be included in the model: Location, Event Number (Exposure Events 1-4 and Non-Exposure Event 1 and 2) and Event Type (Exposure and Non-Exposure Event). A repeated statement will be used to model repeated measures for the time variable.

The denominator degrees of freedom will be determined using the method of Kenward and Roger (1997). In case of non-convergence of the preferred model or memory space issues, the Kenward-Roger method will be replaced by Satterthwaite approximation.

The SAS code for the mixed model to be used is shown below:

```
Proc mixed data=_data_ method=reml;
Class location time event_type;
Model endpoint = location event type event num/ ddfm=kr;
Repeated time/subject=location(event num) type=cs;
Lsmeans event_type / diff alpha=0.05 cl;
Lsmeans location / diff alpha=0.05 cl;
Run;
```

The Geometric LS means and estimate of the ratio of geometric means between Exposure and Non-Exposure Events along with its 95% CI will be presented in tables for Formaldehyde, Acetaldehyde, Acrolein and Crotonaldehyde. The geometric LS means and ratio of geometric means together with their respective CIs are calculated by exponentiating the LSmeans and differences between exposures groups.

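### SAP 14.5.1 holds back the participant-level HeatStick dose for a convergence failure that its linear model cannot have, and its three sample ESTIMATE lines are non-estimable

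*SAP*

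**What the plan says.** SAP 14.5.1 takes the biomarker models of 12.6.1.1 and 12.6.2.2 and plans to "include a covariate for total HeatSticks consumption used during an Event". The sample code also has a `product_use*cumulative_heatsticks` interaction. The planned results are a geometric mean per product-use group and the Exposure/Non-Exposure ratio, evaluated at group averages of the covariates.

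The alternative dose has a single trigger: "If the model fails to converge, then the individual exposure to HeatSticks based on the duration a participant was in the Exposure Event" is to be calculated, and "this will be used in place of an overall cumulative exposure to HeatSticks during the entire Exposure Event".

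The parent model for each biomarker "will be modeled using a linear model in the Compliant Exposure Set", and SAP 10 records that "the random subject effect is removed as there are no repeated measures". The 14.5.1 code has CLASS, MODEL and ESTIMATE statements, but neither RANDOM nor REPEATED.

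**The concern.** A fallback is useful only if its trigger detects the problem it is meant for. Here the trigger is tied to an event that cannot happen in the model as coded. The problem that can happen, an event-level dose that cannot be separated from other event-level covariates, passes unnoticed.

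The ESTIMATE lines are a second, independent fault. They produce every number that 14.5.1 plans to report, and as printed none of them is an estimable function of the model.

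The section was added because questions were raised during study-report review about HeatStick consumption and biomarkers in the Compliant Exposure Set. As specified, it would either return no estimate or, once the code is repaired, return group means that hardly depend on HeatSticks.

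**Working it through.** The documents give no figure to reproduce on this point.

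**1. Can the trigger fire?** With residual variance only, REML has the closed form s² = RSS / (n − rank X). In 500 simulated fits with 0 to 6 event-level air-quality columns, some of them rank-deficient, a numerical optimiser never failed and agreed with the closed form to within 2.3 × 10⁻⁸.

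**2. When is the event-total slope lost?** Inputs:
- Six events: four Exposure and two Non-Exposure (SAP 12.6.2.1.1). Protocol Table 5 lists five.
- The dose is zero at Non-Exposure Events ("cumulative_heatsticks 0 IAQ1 yy" in the code), so it has at most four non-zero values.
- Carbonyls and 3-ethenylpyridine are each "taken as one observation for all participants of the particular event" (SAP 8.2.1). I assume the same for nicotine, NNK and NNN, whose derivation as covariates 8.2.1 does not give.
- SAP Table 8 gives each primary endpoint one mandatory and five candidate covariates of this kind, plus PM2.5 and PM10, which vary by participant.

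Six events support at most six independent event-level columns. Intercept, event type and HeatStick total use three, which leaves 6 − 3 = 3 for air quality. A rank check on a design with 338 rows (2 × 169) agrees:

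| Event-level air-quality columns | Event-total slope | Own-window slope |
|---|---|---|
| 0 to 3 | estimable | estimable |
| 4 to 6 | not estimable | estimable |

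With five events the event-total slope is lost from three columns (5 − 3 = 2). None of this is a convergence failure.

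**3. Are the ESTIMATE lines estimable?** Unprinted coefficients are taken as zero. For Cigarette Smokers:

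| Line | `event_type` printed | needed | `product_use*cumulative_heatsticks` printed | needed |
|---|---|---|---|---|
| Exposure | 1 | 1 0 | none | xx 0 0 |
| Non-Exposure | 0 | 0 1 | none | 0 0 0 (dose is zero) |
| Exposure vs Non-Exposure | 0 | 1 −1 | none | xx 0 0 |

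All three printed lines lie outside the row space of the design for 0 to 6 air-quality columns and for either dose. Adding only the HeatStick interaction repairs the Exposure line. The other two still fail, because they give non-zero `event_type*product_use` coefficients with `event_type` set to zero. With both corrections all three are estimable in every case. If the software spread a missing interaction coefficient equally over the groups, the Exposure line could be computed, but with the average of three slopes in place of the smokers' own. The other two would still fail, because their zeros are written out.

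**4. Does the dose measure change the planned results?** The model has a separate mean for every event-type by product-use cell. The fitted value at a cell's own covariate means is therefore the cell's observed mean, apart from a small shift for setting sex to 0.5/0.5. With 25% of 169 ≈ 42 per cell, the standard error is about 1/√42 = 0.154 residual SDs for a group mean and √(2/42) = 0.218 for the log ratio, whichever dose is used. A simulated design with product use drawn at random gave 0.141, 0.164 and 0.217 (Exposure, Non-Exposure, log ratio), identical under both doses.

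**5. Does it change the slope?** Assumptions: totals of 180, 210, 240 and 270 sticks over 8 h, presence of 2.5 to 4.5 h, one common slope. A participant is then present for 2.5/8 = 31% to 4.5/8 = 56% of the sticks, on average 3.5/8 = 0.4375. Standard errors per 100 sticks, in residual SDs:

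| Air-quality columns | Event total | Own window | Own window × 0.4375 |
|---|---|---|---|
| 1 | 0.249 | 0.435 | 0.190 |
| 2 | 0.302 | 0.480 | 0.210 |
| 3 | 0.511 | 0.583 | 0.255 |

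On a common scale the own-window standard error is smaller by about a quarter, 30% and a half. With assumed totals of 250 to 330 sticks and windows of 2 to 4.2 h, two runs gave reductions in the standard error of slope × mean dose from 45% (0.44 against 0.80) to 65% (0.50 against 1.42).

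**The case against.** **The wording may be loose.** The code is offered as a sample, and SAP 14.4 attributes a failure to converge in the carbonyl analysis to a misspecified model. The team might treat an aliased fit the same way. This stands as a caveat on how the rule would be applied, but the text gives no such instruction.

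**Aliasing is not certain.** SAP 12.6.1.1 drops optional air-quality covariates with p above 0.05, so fewer than four may remain. The number retained is not in the documents.

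**The event total has merits.** It counts the 1 h priming, which deliberately loads the room before passive participants enter, and it resembles the event-level dose in SAP 14.2. Own-window dose is close to stick rate times time present, and duration is already in the model, so its slope leans on how the duration effect differs between events. Both points are fair and justify keeping the event total as a sensitivity analysis.

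**Stronger readings that a reader might infer, and that do not hold:**
- *SAS would set the HeatStick slope to zero, to be read as no effect.* HeatSticks come before the air-quality terms in the MODEL statement, so a later air-quality column would be the one zeroed. The HeatStick coefficient becomes non-unique, not zero, and 14.5.1 does not plan to report it.
- *Own-window dose would narrow the planned intervals.* Step 4 shows no change. The gain in step 5 concerns a slope that is not currently an output.
- *The event total biases the effect downwards.* In simulation a true 0.30 per 100 own-window sticks came back as 0.13 with the event total and 0.31 with own-window dose. That is mostly a change of unit: 0.30 × 0.4375 = 0.131. Power did differ (19% against 28% with one air-quality covariate, residual SD 0.5) but was low for both.

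**Conclusion.** The point holds in two parts. The convergence trigger cannot operate on the model as coded, and the failure that can occur, with four or more event-level air-quality covariates and six events, does not set it off. All three sample ESTIMATE lines are non-estimable as printed. The first part rests on the literal meaning of convergence, on the printed code, and on nicotine, NNK and NNN being event-level averages. The second follows from the code alone, with unprinted coefficients taken as zero.

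Severity is minor. The analysis is post hoc and supportive, the primary estimates are not affected, and the planned means and ratio barely depend on the dose measure once coded correctly. For that reason, changing the dose without also reporting its slope would achieve little.

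**What to change.** In SAP 14.5.1:

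1. Delete the convergence trigger.
2. From the start, fit HeatSticks used at the event between each participant's room entry and last void (zero at Non-Exposure Events). Derive it from the roughly hourly counts in SAP 8.4 and the recorded times; the window matches the passive exposure duration in SAP 5.2. Keep the event total as a sensitivity analysis because it includes priming, and state whether its slope is estimable with the covariates retained.
3. Report the HeatStick slope for each product-use group with its 95% CI. For Cigarette Smokers: `cumulative_heatsticks 1 product_use*cumulative_heatsticks 1 0 0`.
4. Correct the ESTIMATE lines. Exposure: add `product_use*cumulative_heatsticks xx 0 0`. Non-Exposure: `event_type 0 1`, with interaction coefficients 0 0 0. Ratio: `event_type 1 -1` and `product_use*cumulative_heatsticks xx 0 0`. The comparison line in SAP 14.1 also sets `event_type` to zero and should be checked at the same time.

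The cost is SAP wording, one derived variable from data already collected, and a few lines of code. The small downside is the correlation of own-window dose with duration, which should be acknowledged when the slope is reported.
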